### **12.1.3 Description of AEs**

The following guidelines and definitions should be used by the Investigator for the description of an AE when reporting information:

Nature of the AE:	Preferably an overall diagnosis or syndrome, rather than individual symptoms or signs. The Investigator must report adverse events using standard medical terminology. The CRF and source documents should be consistent. Any discrepancies between the subject's own words on his/her own records (e.g., diary card) and the corresponding medical terminology should be clarified in the source documentation.
Date of onset:	Date the AE started.
Pattern:	
Intermittent	The AE recurs with the same intensity at various intervals throughout the entire time period specified. There were intervals within the specified time period when the AE was not present.
Continuous	The AE is present at the same intensity for the entire time period specified. There was no time at which the event abated or was not present during the time period specified.

Intensity:

- |          |  |
|----------|--|
| Mild     | The subject is aware of the sign or symptom (syndrome), but it does not interfere with his/her usual activities and/or it is of no clinical consequence. |
| Moderate | The AE interferes with the usual activities of the subject or it is of some clinical consequence.  |
| Severe   | The subject is unable to work normally or to carry out his/her usual activities, or the AE is of definite clinical consequence.                          |

Action taken with investigational product:

- |                  |  |
|------------------|--|
| Not applicable   | For AEs occurring during the study drug free period.                               |
| No change        | Investigational product dosing remained the same in spite of the AE being present. |
| Dosage increased | Investigational product dose was increased because of this AE.                     |
| Dosage decreased | Investigational product dose was decreased because of this AE.                     |

Temporarily discontinued  
Investigational product was temporarily discontinued because of this AE, either because the subject chose to discontinue the study drug or the physician felt it was in the subject's best interest to temporarily discontinue the investigational product.

Permanently discontinued  

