Investigational product was permanently discontinued because of this AE, either because the subject chose to discontinue the study drug or the physician felt it was in the subject's best interest to discontinue the investigational product.

Other actions taken:  
If action taken other than study drug, the appropriate sections should be completed: Medications, Medical procedures.

Outcome:

- |                       |  |
|-----------------------|--|
| Resolved              | The AE is no longer present at any intensity - completely abated.  |
| Resolved with sequela | The AE is resolved but residual effects are still present.   |
| Ongoing               | The AE is still present at the last contact with the subject. If the AE is marked "ongoing", the outcome date should be blank. |
| Worsened              | The AE is still present but at a heightened intensity. The rule of repetition of AE reporting should be applied.               |

This document cannot be used to support any marketing, distribution application or any extensions or variations thereof.

Fatal	This AE caused or directly contributed to the subject's death.
Date of outcome:	Date the AE abated. If the AE consists of several signs and symptoms (syndromes), the sign or symptom with the longest duration determines the duration of the AE. If the AE is marked "ongoing", the outcome date should be blank.
Relationship to study drug: None	Only applicable when no investigational product was taken or when the subject is taking single-blind placebo, or when the AE can be ascribed with reasonable certainty to another cause (e.g., a gun shot wound).
Unlikely	There are good reasons to think that there is no relationship (e.g., the AE is a known adverse drug reaction of a concomitant medication).
Possible	Equally valid arguments can be considered for or against an implication of the investigational product. For example, the AE: 

• follows a reasonable temporal sequence from the administration of the investigational product.

• follows a known or expected response pattern to the investigational product.

• but could readily have been produced by a number of other factors.

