Probable	The relationship is likely. For example, the AE: 

• follows a reasonable temporal sequence from administration of the investigational product.

• follows a known or expected response pattern to the investigational product.

• is confirmed by improvement on stopping or reducing the dosage of the investigational product.

• could not be reasonably explained by the known characteristics of the subject's clinical state.

This document cannot be used to support any marketing, promotional, or other applications and extensions or variations thereof.

Highly probable

There is a strong relationship. For example, the AE:

- follows a reasonable temporal sequence from administration of the investigational product.
- follows a known or expected response pattern to the investigational product.
- is confirmed by improvement on stopping or reducing the dosage of the investigational product, and reappearance on repeated exposure (re-challenge).

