4.8 Examination of subgroups

Selected summaries will be provided for the following subgroups as specified within each of the following sections;

- Seizure type (Partial Onset Seizures, Primary Generalized Seizures)
- Geographic region (Latin America, North America, Asia/Pacific/Other). A mapping of countries to geographic regions is defined as

| Geographic Region | Country |
|--------------------|---|
| North America | Canada, United States, Puerto Rico |
| Latin America | Brazil, Mexico |
| Asia/Pacific/Other | Australia, Hong Kong, India, Israel, Japan, Singapore, South Africa, Republic of Korea, Taiwan, Tunisia |

- Randomized treatment in the previous study (placebo [PBO], BRV) (TEAEs only)

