11.2.2 General summaries of TEAEs

Pre-treatment AEs will be provided in a subject data listing; no summaries of pre-treatment AEs are planned.

An overall summary of AEs will provide the overall number of TEAEs and the numbers and percentages of subjects with at least 1 TEAE, with a TEAE that led to permanent discontinuation of study drug, with a drug-related TEAE, with a severe TEAE, with a treatment-emergent SAE, and with a drug-related treatment-emergent SAE. The number and percentage of subjects who died will also be summarized. This summary will be provided for all subjects in the Safety Analysis Set and also by subgroup for geographic region and seizure type.

The following summaries of TEAEs will be provided by MedDRA SOC and PT. All summaries are for the combined Evaluation, Down-Titration, and Post-Treatment Periods unless otherwise indicated.

Overall Incidence Summaries

- Incidence of TEAEs
- Incidence of TEAEs by 3-month time interval
- Incidence of TEAEs by study period (Evaluation, Down-Titration, Post-Treatment)
- Incidence of TEAEs for TEAEs occurring in at least 5% of subjects
- Incidence of TEAEs by 3-month time intervals for TEAEs occurring in at least 5% of subjects overall
- Incidence of non-serious TEAEs occurring in at least 5% of subjects

The incidence of TEAEs occurring in at least 5% of subjects will be summarized overall as noted above and also by subgroup for geographic region, seizure type, and randomized treatment from the previous double-blind study.

A subject is included in a 3-month interval if the subject was receiving BRV at any time during that interval based on their duration of exposure to BRV (eg, a subject with exposure for 91 days is included in the time interval for Months 1-3 and Months 4-6). Summaries of AEs by 3-month intervals will include all subjects who are classified into each time interval

as defined above. TEAEs which had onset prior to or on the date of the last dose of BRV are included in summaries by 3-month time intervals.

Maximum Intensity and Causality

- Incidence of TEAEs by maximum intensity
- Incidence of drug-related TEAEs

Serious Adverse Events

- Incidence of treatment-emergent SAEs

Discontinuations due to TEAE

- Incidence of TEAEs leading to permanent discontinuation of study drug

TEAEs of interest

AEs of interest will be identified based on MedDRA search criteria, which are documented outside of the SAP. The following summaries will be provided for AEs of interest:

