- Incidence of TEAEs of interest
- Incidence of TEAEs of interest by 3-month time interval

For the summary by maximum intensity, each subject will be counted at most once per SOC or PT according to the maximum intensity of all AEs within that SOC or PT. Severe intensity will be assumed for AEs for which intensity is not specified.

Drug-related AEs are AEs for which the relationship to study drug is specified as Related or AEs for which relationship is not specified.

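### Does the SAP leave drug-related adverse events undefined by using a category that is not on the protocol's causality scale?

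*SAP*

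**What the plan says.** SAP 11.2.2 gives the only working definition: "Drug-related AEs are AEs for which the relationship to study drug is specified as Related or AEs for which relationship is not specified". It feeds two rows of the overall adverse event summary, in the part of the list that reads "with a drug-related TEAE, with a severe TEAE, with a treatment-emergent SAE, and with a drug-related treatment-emergent SAE". It also feeds one table by system organ class and preferred term, "Incidence of drug-related TEAEs". The overall summary is repeated by geographic region and by seizure type.

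Protocol 12.1.3 introduces its scale with "The following guidelines and definitions should be used by the Investigator for the description of an AE when reporting information". The relationship to study drug then has five grades: None, Unlikely, Possible, Probable and Highly probable. Unlikely is explained as "There are good reasons to think that there is no relationship", Possible as "Equally valid arguments can be considered for or against an implication of the investigational product", and the entry for Highly probable opens with "There is a strong relationship. For example, the AE".

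No link between Related and these grades appears in Protocol 13.1.2 or 13.1.3, or in SAP 3.7 (coding), 3.8 (derived variables) or 14 (amendment).

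**The concern.** A reader who sets the two documents side by side finds that the SAP's key word matches none of the protocol's grades. Applied word for word to the five grades, the rule would leave out events graded Possible, Probable or Highly probable and count only those with no causality recorded. If a programmer supplies a grouping instead, five ordered grades can be split at several points, and the SAP does not say where.

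The SAP does spell out how recorded categories are collapsed for discontinuation reasons (5.1), racial group (6.1) and urinalysis results (11.3.2), so silence on causality can look like an oversight. The study's primary objective is long-term safety, and SAP 4.3 allows interim summaries for submissions. The worry is that an unwritten cut-off might be picked with open-label data in view, or might differ between reports.

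**Working it through.** The plan states no figure that could be reproduced here, so the check compares the texts and then counts the outputs concerned.

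**1. The five grades against the word Related (Protocol 12.1.3)**

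| Grade | Sense of the protocol definition | Side it falls on |
|---|---|---|
| None | no product taken, or another cause reasonably certain | not related |
| Unlikely | good grounds against a link | not related |
| Possible | arguments balanced either way | open |
| Probable | a link is likely | related |
| Highly probable | a strong link | related |

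Grades worded as Related: 0 of 5.

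**2. How many cut-offs are live**

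Five ordered grades allow 5 − 1 = 4 splits: Unlikely and above, Possible and above, Probable and above, or Highly probable alone. The first would count events that the protocol says there is good reason to think unconnected. The last would exclude events that it calls likely to be connected. Neither fits the definitions. That leaves 4 − 2 = 2 splits, which differ only in where Possible goes.

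**3. What the SAP suggests for Possible**

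SAP 11.2.2 counts missing causality as drug-related and treats missing intensity as severe. Both rules resolve doubt towards reporting more. Under the same approach, an event with balanced arguments counts as related, so the split is Possible and above.

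**4. The alternative: a two-level field in the database**

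SAP 11.2.2 speaks of the relationship being specified as Related, which is how one describes a stored value. SAP 2.3 and 2.4 say that enrolment was complete when the SAP was developed, with 668 subjects enrolled, so the database structure was presumably known to its authors. If a Related field exists, the rule needs no mapping. The CRF is not available to confirm this.

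**5. Why the SAP's other mappings do not show an omission here**

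Each answers a stated problem of mixed source data: differing formats across studies for discontinuation reasons, inconsistent collection for race, and differing laboratory scales for urinalysis (13.3.3). A variable recorded in one uniform way would need no such table. The absence of one for causality therefore fits uniform recording as well as it fits an oversight.

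**6. Scope**

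- Groupings of the overall summary: 1 overall + 3 regions (SAP 4.8: "Geographic region (Latin America, North America, Asia/Pacific/Other") + 2 seizure types = 6.
- Rows using the definition: 2.
- Subject counts concerned: 2 × 6 = 12, plus 1 table by system organ class and preferred term.

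This counts table entries. It does not measure bias.

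**7. What does not depend on the definition**

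The primary safety variables in Protocol 13.1.2 and SAP 2.2.1.1 are any treatment-emergent event, withdrawal due to an event, and any serious event. None uses causality. The other safety variables in SAP 2.2.1.2 do not use it either. Protocol 13.1.3 plans no drug-related table, and SAP 3.1 rules out hypothesis testing.

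**The case for a change.** The strongest case for a change is that an SAP exists to remove inference of this kind, and that one sentence would do it. Possible may well be a commonly used grade, and it is the one on which two competent programmers could differ. If the CRF does carry a two-level field, the step from the protocol's five grades to that field is still unwritten, and investigators might make it differently. By contrast, the severe category in the neighbouring rows is an actual grade on the protocol's intensity scale.

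Part of this stands. The two documents do not reconcile their wording, and if five grades are stored, the placing of Possible is left to the analyst. A short note naming the field or the grouping would be tidy.

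The rest is weaker. The word-for-word reading, which drops Highly probable events and keeps only those with missing causality, would produce a table that anyone reviewing it would see was wrong. Nothing in either document suggests that a cut-off was chosen after seeing data or changed between an interim summary and the final report, and SAP 1 limits this plan to the final report. Any inconsistency in how investigators turned five grades into two would arise at data collection, and a sentence in the SAP could not undo it.

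**Conclusion.** The wording differs between the documents, but the stated rule is not shown to give a wrong result. An analyst would either read a recorded Related value or group Possible and above together with missing causality. Both are sensible, and the second follows from the protocol's definitions and the SAP's conservative defaults. Writing the grouping down would only record what the analyst would do anyway, for 12 descriptive subject counts and one table that support no primary or protocol-listed safety variable.

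This conclusion rests on two assumptions. The first is that the database holds either a Related field or the five protocol grades; the CRF is not available to show which. The second is that an analyst facing five grades follows the protocol's definitions and the SAP's conservative defaults. The numerical effect on the counts cannot be bounded, because the documents give no event counts by causality grade and no rate of missing causality. No change to the plan is needed.

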11.3 Clinical laboratory evaluations

Clinical laboratory parameters (blood chemistry, hematology, urinalysis) are assessed at all FEVs, YEVs, EDVs, and at the FV and may also be assessed at unscheduled visits.

11.3.1 Hematology and blood chemistry parameters

Observed values for each planned hematology and blood chemistry parameter will be summarized for Baseline, Study Entry, and each scheduled visit during the Evaluation Period for which laboratory parameters were assessed, Last Value, EDV, and FV. Change from Baseline will be summarized for all post-Baseline time points including EV. Only laboratory parameters planned per protocol will be summarized; results for laboratory parameters not planned per the protocol will only be provided in subject data listings.

The number and percentage of subjects with an on-treatment potentially clinically significant treatment-emergent (PCST) value, PCST low value, and PCST high value will be summarized. This summary will consider all assessments after the first dose of BRV and prior to or on the date of the last dose of BRV. Percentages will be relative to the number of subjects with an on-treatment assessment.

Additionally, the number and percentage of subjects with a PCST value, PCST low value, and PCST high value will be summarized for Baseline, Study Entry, each visit during the Evaluation Period for which laboratory parameters were scheduled to be assessed, EDV, Last Value, and FV. Percentages for each parameter and time point will be relative to the number of subjects with a value at that time point.

PCST criteria (Sections 13.3.1 and 13.3.2) are based on Food and Drug Administration (FDA) Division of Neuropharmacologic Drug Products guidelines with some UCB-defined additions.

Creatinine clearance, when available from the central laboratory, will be provided in subject data listings only and will not be summarized.

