### **9.3.1 Withdrawal Criteria**

Subjects are free to withdraw from the study at any time, without prejudice to their continued care.

Stopping rules and discontinuation criteria for individual subjects may be for example:

- Withdrawal for safety reasons by the Investigator; occurrence of status epilepticus, appearance of a more severe type of seizure, liver enzymes significant increase, and any other significant safety reason.
- Subject and/or Investigator does not think that the investigational drug is effective (i.e., lack or loss of efficacy).
- Lost to follow-up.
- Withdrawal of consent for personal reasons; not related to AE or lack/loss of efficacy.
- Other reason that has to be specified in the CRF.

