3.2.6 Last Value on BRV Treatment

Last Value for QOLIE-31-P, HADS, EQ-5D, and socio-professional data is the last assessment strictly after the date of first dose of BRV and up to and including the YEV at the end of the second year and any EDVs for subjects who did not complete through the YEV at the end of the second year.

Last Value for clinical laboratory parameters, vital signs, and ECGs is the last available result obtained after the first dose of BRV and prior to or on the date of last dose of BRV. All scheduled and unscheduled assessments within this time period will be considered. Last Value will be determined separately for each laboratory parameter.

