3.3 Definition of Baseline Values

Baseline for all study outcomes will be based on baseline from the previous studies. For assessments performed at scheduled and unscheduled visits, Baseline will generally be the last result obtained or prior to the randomization visit of the previous study. Baseline will be defined separately for each hematology, blood chemistry, and urinalysis parameter.

Baseline for the evaluation of seizure frequency and seizure days will be calculated from the core study seizure diary based on the rules defined in Section 3.8.1.

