13.3.2 Blood chemistry parameters

| Parameter | UCB Conventional Units | SI Units | CF |
|-----------------------------|---|---|--------|
| AST (SGOT) | ≥ 3 times of ULN | ≥ 3 times of ULN | N/A |
| ALT (SGPT) | ≥ 3 times of ULN | ≥ 3 times of ULN | N/A |
| ALP | For < 17 y: ≥ 2 times of ULN, if normal range adjusted to the age range; For ≥ 17 y: ≥ 3 times of ULN | For < 17 y: ≥ 2 times of ULN, if normal range adjusted to the age range; For ≥ 17 y: ≥ 3 times of ULN | N/A |
| GGT | ≥ 3 times of ULN, if baseline value ≤ 3 times of ULN | ≥ 3 times of ULN, if baseline value ≤ 3 times of ULN | N/A |
| BUN | ≥ 30 mg/dL | ≥ 10.71 mmol/L | 0.357 |
| Urea | ≥ 60 mg/dL | ≥ 10.02 mmol/L | 0.167 |
| Creatinine | For < 17 y: ≥ 1.5 mg/dL; For ≥ 17 y: ≥ 2.0 mg/dL | For < 17 y: ≥ 132.6 umol/L; For ≥ 17 y: ≥ 176.8 umol/L | 88.4 |
| Creatinine clearance (calc) | For < 12 y: < 70 ml/min (Schwartz) ^(a) For ≥ 12 y: < 70 ml/min (Cockcroft) ^(b) | For < 12 y: < 70 ml/min (Schwartz) ^(a) For ≥ 12 y: < 70 ml/min (Cockcroft) ^(b) | N/A |
| Total bilirubin | ≥ 2.0 mg/dL | ≥ 34.2 umol/L | 17.1 |
| Glucose | ≤ 50 mg/dL or ≥ 180 mg/dL | ≤ 2.775 mmol/L or ≥ 9.99 mmol/L | 0.0555 |
| Total Protein | For ≥ 1 m to < 6 m: ≤ 3.6 g/dL or ≥ 7.8 g/dL For ≥ 6 m to < 17 y: ≤ 4.7 g/dL or ≥ 9.5 g/dL For ≥ 17 y: ≤ 4.5 g/dL or ≥ 9.0 g/dL | For ≥ 1 m to < 6 m: ≤ 36 g/L or ≥ 78 g/L For ≥ 6 m to < 17 y: ≤ 47 g/L or ≥ 95 g/L For ≥ 17 y: ≤ 45 g/L or ≥ 90 g/L | 10 |
| Albumin | For < 17 y: ≤ 2.4 g/dL or ≥ 6.5 g/dL For ≥ 17 y: ≤ 2.5 g/dL or ≥ 6.5 g/dL | For < 17 y: ≤ 24 g/L or ≥ 65 g/L For ≥ 17 y: ≤ 25 g/L or ≥ 65 g/L | 10 |
| Globulin | For < 17 y: ≤ 1.2 g/dL or ≥ 5.0 g/dL For ≥ 17 y: ≤ 1.5 g/dL or ≥ 5.0 g/dL | For < 17 y: ≤ 12 g/L or ≥ 50 g/L For ≥ 17 y: ≤ 15 g/L or ≥ 50 g/L | 10 |
| Sodium | For < 17 y: ≤ 120 mEq/L or ≥ 155 mEq/L For ≥ 17 y: ≤ 115 mEq/L or ≥ 155 mEq/L | For < 17 y: ≤ 120 mmol/L or ≥ 155 mmol/L For ≥ 17 y: ≤ 115 mmol/L or ≥ 155 mmol/L | 1 |
| Potassium | For < 17 y: ≤ 3.0 mEq/L or ≥ 6.5 mEq/L For ≥ 17 y: ≤ 3.0 mEq/L or ≥ 5.8 mEq/L | For < 17 y: ≤ 3.0 mmol/L or ≥ 6.5 mmol/L For ≥ 17 y: ≤ 3.0 mmol/L or ≥ 5.8 mmol/L | 1 |
| Calcium | For < 17 y: ≤ 7 mg/dL or ≥ 11.5 mg/dL For ≥ 17 y: ≤ 7 mg/dL or ≥ 15.5 mg/dL | For < 17 y: ≤ 1.75 mmol/L or ≥ 2.875 mmol/L For ≥ 17 y: ≤ 1.75 mmol/L or ≥ 3.875 mmol/L | 0.25 |

This document cannot be used for marketing authorizations, clinical trial extensions or variations thereof.

| | | | |
|--|---|---|--------|

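### The planned laboratory tables count transaminase and bilirubin abnormalities separately, so they do not give the number of subjects who had both

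*SAP*

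**What the plan says.** SAP 11.3.1 plans four kinds of chemistry summary: observed values, change from Baseline, an on-treatment PCST count, and PCST counts by time point. For the on-treatment count it says that "The number and percentage of subjects with an on-treatment potentially clinically significant treatment-emergent (PCST) value, PCST low value, and PCST high value will be summarized".

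That sentence does not itself name the unit of counting. The surrounding text does:

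- SAP 11.3.1, observed values: "Observed values for each planned hematology and blood chemistry parameter will be summarized for Baseline, Study Entry, and each scheduled visit during the Evaluation Period".
- SAP 11.3.1, by-visit PCST counts: "Percentages for each parameter and time point will be relative to the number of subjects with a value at that time point".
- SAP 3.3: "Baseline will be defined separately for each hematology, blood chemistry, and urinalysis parameter".
- SAP 3.2.6: "Last Value will be determined separately for each laboratory parameter".
- SAP 13.3.2 gives free-standing limits, for example "AST (SGOT) | ≥ 3 times of ULN". ALT has the same limit, and total bilirubin has an absolute limit of 2.0 mg/dL.

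Neither document defines a criterion, cross-tabulation or plot that combines a transaminase with bilirubin. Protocol 13.1.3 does plan a listing of possibly clinically significant laboratory abnormalities as well as summaries by period and visit, and SAP 3.1 plans subject listings of source data and key derived variables.

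**The concern.** A transaminase rise together with a bilirubin rise in one person is a different finding from two isolated rises in two people. Separate rows show how many subjects had each abnormality, but not how many had both.

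Long-term safety is the primary objective (Protocol 7.1, SAP 2.1.1) and laboratory tests are a named safety variable. Protocol 9.3.1 gives "liver enzymes significant increase, and any other significant safety reason" among its examples of safety reasons for withdrawal. That wording concerns enzymes and not bilirubin, so it shows that the liver is of interest, not that a combined criterion was promised.

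The study is single-arm and all summaries are descriptive (SAP 3.1), so the counts in the tables are the safety result. As planned, the tables could not support a statement that no subject had both abnormalities, nor give the number if some did.

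**Working it through.** The plan states no figure for this point, so there is none to reproduce. The question is whether the planned tables determine the joint count.

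**Inputs.** 668 enrolled subjects (SAP 2.4), used only as an illustrative denominator; SAP 11.3.1 uses subjects with an on-treatment assessment. Limits are from SAP 13.3.2. The documents give no PCST rates, so every count below is assumed.

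**Range of the overlap.** Let a be the number of subjects with ALT or AST at or above its limit, b the number with bilirubin at or above its limit, and N the number assessed. The number with both lies between max(0, a + b − N) and min(a, b). For a = 10, b = 8, N = 668:

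- lower end: max(0, 10 + 8 − 668) = 0
- upper end: min(10, 8) = 8

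Even a is not a planned entry, because ALT and AST have separate rows. The ALT-or-AST count lies between the larger of the two and their sum.

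**What that range means as a percentage** (exact Clopper-Pearson 95% limits):

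| Subjects with both | Percentage of 668 | 95% limits |
|---|---|---|
| 0 | 0% | 0 to 0.55% |
| 2 | 0.30% | 0.04% to 1.08% |
| 8 | 1.20% | 0.52% to 2.35% |

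**Can the tables really be the same?** Pairs of data sets were built with N = 668 and five visits. ALT and AST rises were placed in the same a subjects. Bilirubin rises were given either to b of those subjects or to b different subjects, with the same set of values at each visit. The statistics compared were subjects with any PCST value, PCST counts by visit and at the last visit, and mean, SD, median, quartiles, minimum and maximum.

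| a | b | Joint count, first set | Joint count, second set | Tables identical |
|---|---|---|---|---|
| 3 | 2 | 2 | 0 | yes |
| 7 | 3 | 3 | 0 | yes |
| 13 | 7 | 7 | 0 | yes |
| 20 | 13 | 13 | 0 | yes |
| 33 | 20 | 20 | 0 | yes |

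**What the by-visit tables add.** If a_t and b_t are the counts at visit t, same-visit coincidences at scheduled visits cannot exceed the sum over t of min(a_t, b_t). If all transaminase rises fell at Month 6 and all bilirubin rises at Month 12, that sum is 0. The number of subjects with both at some time on treatment would still be anywhere from 0 to 8. So these tables can narrow the same-visit range, but they do not identify subjects.

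**The case against.** The strongest reply is that the information is not lost. Protocol 13.1.3 plans a listing of these very abnormalities, and SAP 3.1 adds source-data listings. With counts like 10 and 8 the cross-match is short. This stands, and it limits the point to the summary tables: what is missing is a planned, reproducible count, not the data.

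A reader might infer that combined liver injury would go unseen. The documents do not support that. An abnormal laboratory finding can be reported as an AE (Protocol 12.1.1). SAEs, TEAEs leading to discontinuation and TEAEs of interest are all tabulated (SAP 11.2.2), and a programme-wide Safety Data Review is running (Protocol 13.3.2). None of these counts concurrent laboratory rises, however. The search criteria for AEs of interest lie outside the SAP, so their hepatic content can be neither confirmed nor ruled out.

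A reader might also infer that isolated enzyme rises here come from concomitant AEDs, which would make separate rows a particularly unspecific way to look for liver injury by BRV. Neither document says so, and the point does not need it.

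Two objections to the form of a remedy are fair. First, a same-sample count alone would be too narrow: after Month 6, subjects from the confirmatory studies have scheduled laboratory tests only every 6 months (Months 12, 18 and so on), so rises in neighbouring samples would be missed. Second, a row defined by ALP below its PCST limit would be misleading, because that limit is 3 x ULN from age 17 and a value of 2.9 x ULN would count as below it. The fix allows for both.

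**Conclusion.** The point holds for the planned summary tables: they do not give the number of subjects with both a transaminase and a bilirubin PCST value. For assumed counts a and b, that number can be anything from 0 to min(a, b). In the assumed example of 10 and 8 among 668 it is 0 to 8 subjects, or 0% to 1.2%.

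This rests on reading the on-treatment PCST count as one row per parameter, which the rest of SAP 11.3.1 and SAP 13.3.2 support. Read instead as any PCST value across all parameters, it would still not show which abnormalities coincided. The size is illustrative only, since real rates and the number assessed are not in the documents.

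Nothing planned is invalid, and the SAP does not contradict the protocol here. It is an omission worth correcting because safety is the primary objective and the count is easy to obtain.

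**What to change.** Add to SAP 11.3.1 one on-treatment table for the Safety Analysis Set, with subjects having an on-treatment assessment as the denominator. Give the number and percentage of subjects with:

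- (a) ALT or AST ≥ 3 x ULN;
- (b) total bilirubin ≥ 2.0 mg/dL;
- (c) both (a) and (b) in the same sample;
- (d) both (a) and (b) at any time on treatment.

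Add a listing of the subjects in (c) or (d) with sample dates, Baseline values and concurrent ALP. Baseline values are needed because the AST, ALT and bilirubin limits carry no baseline condition, so a pre-existing elevation could count. Showing ALP as a value avoids relying on its PCST limit.

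The cost is one extra table and one short listing. The limits are already in SAP 13.3.2, and Protocol 11.1.14 collects all the tests in one central-laboratory chemistry panel, so no new data are required.
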